# **Data Analytic Plan for Aim 2**

Efficacy. Descriptive statistics (means, SDs, frequencies, percentages) will be calculated and compared for overall group differences via chi-square tests, ANOVA models, or nonparametric equivalents, as necessary, for baseline variables. Pairwise differences will be explored for variables that show a significant overall group difference. Significant baseline demographic differences between groups will be included as covariates in regression analyses. Generalized Estimating Equation (GEE) modeling will be used to examine group differences (Moodivate, Moodivate + EHR, TAU) in depression (BDI-II) over time along with the interaction between group and time adjusting for baseline differences and baseline depression. All models will include a clustering effect to account for the clinic from which the participant was recruited. Sex will be included as a covariate in all models. GEE affords examination of specific contrasts (i.e., Moodivate vs. TAU at a specific time point) as well as overall effects of group, time, and the interaction between group and time, while also accounting for repeated measures within participants and any clustering within clinics.

Missing Data. Missing data can be a concern in longitudinal studies, and GEE modeling can assist by including participants with partially complete follow-up data instead of requiring complete follow-up data from all participants. All randomized participants will be included in primary analyses, and imputation methods will be used to accommodate missing data if missing data is >10%. For small amounts of missing data (<10%), these data points will be excluded from modeling, as the sample size has been inflated to account for some attrition. Additionally, sensitivity analyses will be done using only participants with complete follow-up data, with results compared to primary analyses. Attrition will also be assessed to determine whether dropout is differential by group to identify any potential bias in group assignment.

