The economic evaluation of Moodivate and Moodivate + EHR relative to TAU will be conducted from the budgetary perspective, as the primary focus herein is on the financial attractiveness of Moodivate for commercial launch. Health systems and payors in particular may be more likely to adopt Moodivate if it is established as either 1) cost-saving or 2) providing a clinical benefit cost-effectively. To examine cost-saving, we will first conduct a cost-benefit analysis by comparing changes in BDI-II scores and any reduction in all-cause and mental health-related healthcare expenditures for a 12-month period before and after Moodivate implementation (or Moodivate + EHR) relative to TAU. Cost data for all inpatient, outpatient and emergency department (ED) care will be obtained from the MUSC primary care ICCE billings department. As study participants may seek care outside of the MUSC system, we will also obtain all-payors' claims data from South Carolina's Revenue and Fiscal Affairs Office (RFA). RFA maintains data on inpatient and ED utilization across the state regardless of patients' point of care. The case for Moodivate (with or without EHR) adoption and commercialization will be the strongest if the product reduces healthcare expenditures while also improving depressive symptoms.

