Even if the app is not cost-saving, there is a compelling case for adoption if the intervention improves outcomes cost-effectively. For cost-effectiveness analyses, we will follow gold standard procedures and calculate the incremental cost effectiveness ratio (ICER), defined as the additional cost per additional outcome desired. Because there are three groups, we will order interventions from most to least costly, likely to be (a) Moodivate + EHR, (b) Moodivate, and (c) TAU. We will then calculate the ICERs for (a) vs. (b) and (b) vs. (c). Because this is an RCT, our ICER is straightforward: (cost of Moodivate + EHR – cost of Moodivate) / (BDI-II score of Moodivate + EHR – BDI-II score of Moodivate). This formula is replaced with corresponding variables when the comparison is Moodivate vs. TAU. We will assume (but verify) that the three groups have similar characteristics so that observed differences in outcomes reflect differences in the intervention. If group differences are evident, a generalized linear model will be used to adjust for between-groups differences. Any intervention that is "dominated" (i.e., is more expensive but yields less desirable result) will be eliminated from consideration. Likewise, we will also eliminate any intervention that is "extendedly dominated" (i.e., an intervention that has an ICER higher than the next most effective intervention). For example, if the ICER of Moodivate vs. TAU is higher than the ICER of Moodivate + EHR vs. Moodivate, we will eliminate Moodivate as being extendedly dominated and calculate the ICER of Moodivate + EHR versus TAU directly. All costs will be converted to net present value at standard discount rates (3% and 5%). Probabilistic sensitivity analyses using Monte Carlo microsimulations will test the robustness of results with differing ranges of costs and treatment effectiveness. Ranges will be based on confidence intervals estimated in Aim 2 outcomes. For cost data, MPT will estimate ranges of app development and distribution costs. An acceptability curve of the costeffectiveness of any non-dominated intervention will demonstrate the probability of app cost-effectiveness under different levels of willingness to pay.

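### Aim 3 adjusts for baseline unconditionally in neither of its two steps, which costs precision and leaves the ICER base case on a different estimator from its sensitivity ranges

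*Combined protocol and SAP*

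**What the plan says.** Section 11.0, Data Analytic Plan for Aim 3, describes two separate analyses.

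- **Cost-benefit step.** The spending contrast covers "healthcare expenditures for a 12-month period before and after Moodivate implementation (or Moodivate + EHR) relative to TAU". BDI-II is handled in the same way, as a change rather than a score. Both cost and BDI-II therefore enter as before-after changes, contrasted with TAU. Section 10.0 (Aim 3: Cost-Effectiveness) repeats this without the 12-month window.
- **ICER step.** The plan introduces it with "Because this is an RCT, our ICER is straightforward" and gives the ratio as "cost of Moodivate + EHR – cost of Moodivate) / (BDI-II score of Moodivate + EHR – BDI-II score of Moodivate". The formula subtracts no prior year, has no baseline BDI-II term and names no timepoint. Adjustment is conditional: "If group differences are evident, a generalized linear model will be used to adjust for between-groups differences". For the probabilistic sensitivity analysis, "Ranges will be based on confidence intervals estimated in Aim 2 outcomes".

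The Data Analytic Plan for Aim 2 estimates the BDI-II effect by GEE, "along with the interaction between group and time adjusting for baseline differences and baseline depression", with sex as a covariate and clustering by clinic. Section 4.0 has BDI-II measured at baseline as well as follow-up. Section 10.0 randomises 1:1:1, stratified by baseline depressive symptoms and concurrent depression treatment.

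**The concern.** In a randomised trial the prior-year value is useful because it predicts the outcome. Subtracting it fixes its coefficient at one, whatever the data show, and so brings in its noise. Using it as a covariate lets the data set the coefficient. If prior and later cost are only weakly correlated, subtraction can be worse than ignoring the prior year altogether.

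The ICER has a different problem. Its effect is written as a raw difference in BDI-II score, although Aim 2 estimates the same contrast with baseline adjustment. With follow-ups at Weeks 1 to 8 and Week 12, nine different denominators fit the formula. The conditional model does not settle this. The precision gained from a prognostic baseline does not depend on observed imbalance, and a rule triggered by the data, with no threshold or covariates named, leaves the estimator open until the data are seen.

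These estimates feed the dominance and extended-dominance rules and the commercial case. One ICER concerns Moodivate + EHR vs. Moodivate, a contrast whose size the sample-size section says cannot yet be estimated. A ratio with a small denominator is sensitive to noise in it.

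**Working it through.** **Plan's own figure.** Aim 3 states no sample size, standard deviation, correlation or power, so there is nothing to reproduce.

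**Inputs**
- Equal allocation (section 10.0).
- Phase I SDs of BDI-II change, 13.2 and 15.0 (Sample Size Estimation). Pooled: √((13.2² + 15.0²)/2) = 14.13.
- 160 completers per arm, from that section's 200 per group less 20% attrition.
- r, the correlation between baseline and follow-up. It is not in the documents and is **assumed**, from 0.2 to 0.7.

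**Formulas** (large samples, equal baseline and follow-up variance σ², per-arm variance)
- Follow-up only (raw): σ²
- Change score: 2σ²(1 − r)
- Linear baseline adjustment: σ²(1 − r²)

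Hence change/adjusted = 2/(1 + r), raw/adjusted = 1/(1 − r²) and change/raw = 2(1 − r).

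| Assumed r | Change/adjusted variance (SE) | Raw/adjusted variance (SE) | Change/raw variance |
|---|---|---|---|
| 0.2 | 1.67 (+29%) | 1.04 (+2%) | 1.60 |
| 0.3 | 1.54 (+24%) | 1.10 (+5%) | 1.40 |
| 0.5 | 1.33 (+15%) | 1.33 (+15%) | 1.00 |
| 0.6 | 1.25 (+12%) | 1.56 (+25%) | 0.80 |
| 0.7 | 1.18 (+8%) | 1.96 (+40%) | 0.60 |

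Under equal variances, the change score is noisier than ignoring the prior year whenever r is below 0.5.

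**Skewed costs.** A simulation with log-normal costs, 200 per arm and linear adjustment gave change/adjusted variance ratios of 1.67, 1.47 and 1.27 at Pearson correlations of about 0.20, 0.38 and 0.59. The closed form gives 1.67, 1.45 and 1.26. The simulation contained no zero costs.

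**BDI-II in points.** Fix the change SD at 14.13, so σ = 14.13/√(2(1 − r)), and take the SE of a group difference as SD × √(2/160).

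| Assumed r | σ | SE raw | SE change | SE adjusted |
|---|---|---|---|---|
| 0.3 | 11.94 | 1.34 | 1.58 | 1.27 |
| 0.5 | 14.13 | 1.58 | 1.58 | 1.37 |
| 0.7 | 18.24 | 2.04 | 1.58 | 1.46 |

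**Which ratio applies where.** Change/adjusted applies to the cost-benefit step, for both cost and BDI-II. Raw/adjusted applies to the ICER point estimate: to its denominator, and to its numerator if that is follow-up cost alone.

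**The case against.** **The plan does not fix the estimators.** A before-after comparison relative to TAU does not rule out a model with prior cost as a covariate, and the ICER text never says unadjusted. This stands in part. Subtraction and a raw difference are the natural readings, not explicit methods. If a covariate model is intended, one sentence would settle it.

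**The plan already has a generalized linear model.** It does, but only when differences are evident, so the precision gain is not secured.

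**Effect uncertainty is already adjusted.** This stands. A reader might infer that the raw denominator widens the effect intervals in Aim 3. The documents do not support that: the only effect ranges described come from Aim 2, whose model adjusts for baseline depression. What is noisier is the base-case point estimate, and it need not sit at the centre of those ranges.

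**Both contrasts are valid under randomisation.** This also stands. Raw and adjusted mean differences at the same timepoint target the same quantity, and stratification on baseline depressive symptoms limits chance imbalance in BDI-II. The raw/adjusted ratios are therefore towards the upper end for BDI-II. Part of that excess is an overstated SE if the analysis ignores the strata, not real extra variability.

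**No test or power is at stake.** Aim 3 states no hypothesis test, alpha or power, so this bears on efficiency and coherence rather than error rates.

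**Conclusion.** The point holds as a loss of precision and consistency, not of validity. For the cost-benefit step, the change score has 1.67 to 1.18 times the variance of the adjusted estimate over assumed correlations of 0.2 to 0.7. The sizes rest on equal variances, large samples and correlations that the documents do not give. The direction does not depend on the correlation: in large samples, linear baseline adjustment is at least as precise as either alternative. For the ICER, the base-case effect as written is not the Aim 2 estimate, although its sensitivity ranges are drawn from Aim 2.

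Two stronger readings should be resisted. A reader might infer that Aim 3 divides a prior-year-subtracted cost by a raw BDI-II difference. No written analysis does so: the before-after cost belongs to the cost-benefit step, which pairs it with change in BDI-II, and the ICER numerator subtracts no prior year. The change-score ratios therefore do not carry over to the ICER. A reader might also infer that the cost-effectiveness result would be biased; nothing in the plan points to that.

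This should be changed because it is free, not because the analysis would otherwise fail.

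**What to change.** Amend the Data Analytic Plan for Aim 3 as follows.

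1. **Cost, both steps.** Estimate incremental cost from the 12 months after randomisation, with prior 12-month cost as a prespecified covariate regardless of observed imbalance. Report the adjusted mean difference. Use a method that accepts skewed and zero costs, for example linear regression with bootstrap or robust standard errors, a quasi-likelihood generalized linear model, or a two-part model. A plain gamma likelihood does not admit zeros, which are possible for mental health-related expenditure.
2. **Effect.** Use the Aim 2 baseline-adjusted GEE contrast at one named timepoint (Week 12, for example) in the cost-benefit step, the ICER base case and the sensitivity analysis.
3. **Conditional rule.** Replace the adjustment that depends on evident group differences with the prespecified covariates above.

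The cost is SAP wording only. Prior-year expenditure and baseline BDI-II are already to be collected, and no visit, participant or data source is added.

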#### **Data Management**

Regarding questionnaire data, data will be obtained for research purposes only. All data will be collected, stored, and managed via REDCap, which is a secure, web-based application designed exclusively to support data capture for research studies. REDCap provides secure, web-based flexible applications, including real time validation rules with automated data type and range checks at the time of entry. The underlying database is hosted in a secure data center at MUSC, a secure environment for data systems and servers on

campus, and includes redundancy, failover capability, backups and extensive security checks. The system has several layers of protection including user/group account management, "Data Access Groups" which allow data to be entered by multiple groups in one database with segmented user rights for entered data, audit trails for all changes, queries and reports, and Secure Sockets Layer (SSL) encryption. Name and relevant contact information will be obtained to provide compensation and every effort will be made to maintain subject confidentiality, in accordance with HIPAA. All data will be identified only by code numbers (participant IDs). Participant IDs will be linked to participants' names in a password-protected file that is accessible only to the PI and trained research staff.

Deidentified data from this study will be submitted to the National Institute of Mental Health Data Archive (NDA) at the National Institutes of Health (NIH).

## 12.0 Provisions to Monitor the Data to Ensure the Safety of Subjects (if applicable)

This section is based on the recommendations in NIDA's "Guidelines for developing a Data and Safety Monitoring Plan" as well as NCI's "Essential Elements of a Data and Safety Monitoring Plan for Clinical Trials Funded by the National Cancer Institute".

#### Summary of the Protocol

This application consists of a 3-Aim proposal. In Aim 1, both providers (n=10) and adults with depressive symptoms (n=10) will be recruited for iterative usability testing of Moodivate and the Moodivate EHR provider portal. In Aim 2, we will conduct a three-arm randomized controlled trial (n=695) to examine the efficacy of 1) Moodivate vs. 2) Moodivate + EHR integration vs. 3) TAU for the treatment of depressive symptoms within primary care. In Aim 3, we will conduct a cost-effectiveness analysis of implementing Moodivate and Moodivate + EHR integration within primary care practices relative to TAU.

## Trial Management

The study will be managed from the Addiction Sciences Division within the Department of Psychiatry and Behavioral Sciences at the Medical University of South Carolina (MUSC). Recruitment, data collection, data management, and treatment provision will be coordinated and centrally managed at our research lab at MUSC and will be implemented within local Family Medicine/Primary Care clinics that are part of MUSC's Primary Care ICCE.

#### Data Management and Analysis

Participants will enter data in REDCap, a secure, web-based application designed exclusively to support data capture for research studies. REDCap provides: 1) an intuitive interface for data entry (with data validation); 2) audit trails for tracking data manipulation and export procedures; 3) automated export procedures for seamless data downloads to common statistical packages (SPSS, SAS, Stata, R); 4) procedures for importing data from external sources; and 5) advanced features, such as branching logic and calculated fields. These procedures are effective in minimizing data entry errors (e.g., missing or errant data). All data from Moodivate will be stored on a HIPAA-compliant server and data will be transmitted securely via industry standard protocols to Epic (MUSC's EHR). Data analytic plans are outlined above.

#### Quality Assurance

Accuracy and completeness of the data collected will be ensured by weekly review. The REDCap system does not accept outliers, illogical response patterns, etc. The PI and research assistant will have weekly meetings to discuss any qualitative comments received during data collection and any problems in data collection. The PI will examine the database for potential irregularities monthly. Initial data analyses will

examine distributions of variable scores and comparability of baseline characteristics across conditions (for Aims 2 and 3) in case analyses need to be adjusted for these. Confidentiality procedures are outlined above.

#### Regulatory Issues

This study will be registered on clinicaltrials.gov. The study does not require an IND from the FDA. All serious AEs will be reported to the MUSC Committee on Human Research within 48-hours. Follow-up of all unexpected and serious AEs will also be reported. All AEs will be reviewed weekly by the PI and yearly by the IRB. Any significant actions taken by the local IRB and protocol changes will be relayed to the funding agency. We estimate the significant AE rate to be very low (< 5%). If monthly monitoring indicates the rate is above this, we will convene a meeting of the DSMB. Potential conflicts of interest (COI) will be reported using the rules of MUSC's COI committee.

#### Trial Safety

The potential risks and benefits and methods to minimize these risks are outlined in the "Protection of Human Subjects" section. We will determine if any AEs result in dropouts or are serious according to FDA guidelines. The PI ([name]) will serve as the Program Manager for AEs. All unexpected AEs will be monitored while they are active to determine if treatment is needed. We anticipate that AEs will be rare given that the Moodivate app is non-invasive and that all participants will be engaged with current healthcare. Nonetheless, any AEs will be coded on a weekly basis using the FDA's COSTART rules and entered into a database. For each weekly study meeting, the research assistant will prepare a summary of all AEs, including their severity, whether they caused a dropout, required treatment, and presumed relation to app utilization. The PI will review this at the weekly study meeting (or before if more urgent). At the weekly meeting (or before if urgent), the research assistant will report any premonitory symptoms to suggest emergence of a serious psychiatric condition (e.g., suicidality). Drs. [name] and [name], board-certified Family Medicine physicians, will be available on an ad-hoc basis for on-site medical supervision for any issues that cannot be resolved by [name].

Study procedures will follow as much as possible the FDA's Good Clinical Practice Guidelines and our research team has found Spilker's comprehensive text on conducting clinical trials to be useful. We will encourage participants to notify their physicians that a) they are in a randomized controlled research study examining a treatment for depressed mood, and b) the physician should contact the PI directly if the physician has any questions.

The research assistants will be instructed not to reveal whether a person is a participant in the study and will report to the PI any outside requests for information about a participant or any breaches in confidentiality. All requests by participant's physicians and other medical providers will be referred directly to the PI.

#### Trial Efficacy

The Data and Safety Monitoring Board (see below) may request a blinded interim efficacy report (blinded to the PI and research team) for review while the trial is ongoing. Final (fully unblinded) efficacy analysis will occur after all participants have completed all follow-ups.

## Data and Safety Monitoring Plan Administration

The PI will be responsible for monitoring the trial, with additional oversight provided by study co-Investigators. The PI will examine monthly the outcomes database for missing data, unexpected distributions or responses, and outliers. The PI will check weekly the AE database prepared by the research assistant immediately prior to the lab meeting. A DSM report will be filed with the IRB and funding agency on a yearly basis, unless greater than expected problems occur. The report will include participant characteristics, retention and disposition of study participants, quality assurance issues and reports of AEs, significant/unexpected AEs and serious AEs. We will report efficacy at the end of the trial.

#### Data and Safety Monitoring Board Plan

We will create a Data and Safety Monitoring Board (DSMB), comprised of 3 clinicians with expertise in depression treatment, primary care, and clinical trials, as well as a statistician. The DSMB will meet annually (more frequently as needed for emergent situations) to review any AEs related to the study, as well as review any data management related errors. The board may be called at any point if needed for unexpected, serious AEs, etc. Modification will be made in the procedures and/or the protocol if necessary based on the findings of the board.

# 13.0 Risks to Subjects

The potential risks in this study include those related to: a) depressive symptoms, b) clinical deterioration, c) confidentiality, d) potential data breach from the app database, and e) frustration. All risk mitigation strategies outlined below were approved by the MUSC IRB and implemented with success during our Phase I trial.

- a) Depressive symptoms: Depressive symptoms will be monitored via the BDI-II. All participants will complete the BDI-II weekly online via a REDCap survey that is accessible via mobile phone web browsers. All participants will own smartphones. Thus, all participants should have access to the online BDI-II assessments.
- b) Clinical deterioration: [name] and her research team will monitor participant PHQ-9 and BDI-II scores for possible clinical deterioration (i.e., increasing depressive symptoms and/or the development of suicidal ideation) throughout the course of the study as participants complete the PHQ-9 and BDI-II weekly. Clinical deterioration will be defined as an increase of 10 or more points on the BDI-II from the baseline BDI-II assessment or a response of "I would like to kill myself" or "I would kill myself if I had the chance" on the suicidal thoughts or wishes item of the BDI-II. Our team has developed alerts within REDCap reports that the investigative team checks daily to determine whether a participant completed a BDI-II assessment and evidenced evidences clinical deterioration. This system has now been implemented with success across multiple studies. In the event that a participant evidences clinical deterioration, [name] will contact the participant via phone and will provide referrals for local mental health resources for depression treatment. [name] will suggest that the participant seek treatment and then will follow-up with the participant via phone one week later. In the event that a participant reports suicidal ideation either during study screening or during subsequent assessments. [name] will 1) page the participant's attending primary care provider and 2) complete a risk assessment with the participant via phone. [name] will query the participant for details regarding the suicidal ideation, including a likelihood of harming oneself imminently and a plan for committing suicide. If the participant reports an imminent likelihood of harming him/herself or a plan for committing suicide, [name] will call emergency services and will remain on the phone with the participant until emergency services arrive. Contact information including home address will be collected during study screening and will be provided if necessary to emergency services personnel. [name] is a licensed clinical psychologist and has more than 10 years of experience conducting suicide risk assessments. In the event that a participant evidences clinical deterioration, the participant will be allowed to continue in the trial, but we will recruit an additional participant for data collection purposes.
- c) Confidentiality: Participants will be made aware of limits to confidentiality at the beginning of screening and during informed consent which includes a report of suicidal or homicidal intent or report of

abuse or neglect. If the participant reports suicidal or homicidal intent or abuse/neglect during screening or at any point during the trial, [name] will take appropriate action as outlined by the MUSC IRB, NIH, and the State of South Carolina, which may include paging the participant's physician, contacting the authorities and/or pursuing involuntary commitment at a mental health facility. If participants present no imminent danger but also need more extensive treatment of mental health concerns, they will be given appropriate referrals.

- d) Data breach: Although health information will be collected within Moodivate (e.g., daily mood ratings, activities, values), personally identifiable information will intentionally not be collected within the app (e.g., name, phone number, email address, etc.), and thus we will not collect nor will we retain protected health information (PHI). In the event of a data breach, it is important to note that health information will not be able to be tracked back to specific individual users. By refraining from collecting PHI within the mobile app, we ensure HIPPA compliance while also protecting the identities of our users. In the event of a data breach, all app users will be notified via email.
- **e)** Frustration: Participants may become frustrated while completing questionnaires or while using Moodivate. Participants will be informed that they may refuse to answer any question(s) that they do not wish to answer and that they may discontinue use of Moodivate at any time.

Since patients will all currently be receiving medical care at MUSC, there are no additional risks associated with participation in this study.

